### 3.3 TREATMENT MODIFICATIONS

#### 3.3.1 General guidelines for treatment modifications at the time of re-treatment

##### Adverse Events:

The descriptions and grading scales found in the revised NCI Common Terminology Criteria for Adverse Events (CTCAE) version 3.0 will be utilized until December 31, 2010 for AE reporting. CTCAE version 4.0 will be utilized beginning January 1, 2011. All appropriate treatment areas should have access to a copy of the CTCAE version 4.0. A copy of the CTCAE version 4.0 can be downloaded from the CTEP web site (<http://ctep.cancer.gov>).

Dose adjustments will be made according to the guidelines below, with dose levels defined as follows:

Level -1:	4.5 mg/m  /day x 5 days
Level 1:	6 mg/m  /day x 5 days

There is only one dose reduction allowed. Patients who have continued toxicities on the reduced dose level (4.5 mg/m^2/day x 5 days) will be removed from study.

#### 3.3.2 Treatment modifications for hematologic toxicities and delay in start of cycle

Doses will be modified if the start of a cycle is delayed more than two weeks (in all cycles after the first cycle, the day 1 dose will be administered only when the ANC is greater than 1000/mm^3 and the platelet count is above than 75,000/mm^3). There will be no dose modification for a delay of two weeks or less.

Doses will also be modified based upon the nadir from the previous cycle according to the following guidelines.

Toxicity:	Dose Adjustment:
ANC $\leq$ 500/mm  for $\geq$ 4 days	Reduce ixabepilone one dose level
Platelet count $\leq$ 50,000/mm 	Reduce ixabepilone one dose level
Delay in starting cycle > 2 weeks	Reduce ixabepilone one dose level

#### 3.3.3 Treatment modifications for non-hematologic toxicities

If non-hematologic grade 3 and 4 toxicities occur, treatment will be interrupted until the toxicity:

- Resolves to grade 2 or less if the toxicity is fatigue, anorexia, or fingernail changes, or

- Resolves to grade 1 or less if the non-hematologic toxicity is other than those enumerated in the previous bullet.

If toxicity does not resolve to  $\leq$  grade 2 within two weeks, that patient will be removed from study. Once a toxicity resolves to the required grade as enumerated above, treatment may be restarted and drug dosing modified according to the guidelines below. However, patients who experience grade 4 non-hematologic toxicities will be individually evaluated with regard to continuation of treatment. These patients should not be restarted on therapy once toxicity resolves unless there is some clear indication of patient benefit in the form of objective tumor response. In these cases, the reason(s) for restarting therapy will be clearly indicated in the case report form, and the medical record, and the risks and potential benefits will be discussed with the patient.

Dose modifications for non-hematologic toxicities will be based upon the toxicity from the previous cycle. All toxicities must resolve to grade 2 or less as indicated above prior to the initiation of a subsequent cycle. The following apply:

Maximum toxicity grade:	Ixabepilone dose
1	Unchanged
2	Unchanged
3 Note 1	Reduce ixabepilone one dose level
4 Note 2	Reduce ixabepilone one dose level

Note 1: If grade 3 fatigue occurs but resolves to grade 2 or less by the start of the next cycle, the dose of ixabepilone will remain unchanged.

Note 2: As noted above, patients who experience grade 4 non-hematologic toxicities will be individually evaluated with regard to continuation of treatment. Exceptions to the need for individual evaluation include patients with a grade 4 toxicity included in the list that follows, in which case adjustments will be made in accordance with the guidelines listed above.

Grade IV hypocalcemia with normal ionized calcium

Grade IV hypokalemia that responds to medical intervention

Grade IV hypomagnesemia that responds to medical intervention

Grade IV hypophosphatemia that responds to medical intervention

Grade IV sepsis with source identified and treatment successfully instituted

Grade IV stomatitis

### 3.4 CORRELATIVE STUDIES

#### 3.4.1 Biopsies for Research Purposes

As indicated in the introduction, every attempt will be made to recruit patients with disease that can be sampled by biopsy. In these patients, every attempt will be made to obtain tissue before the start of treatment and after the completion of the fourth or fifth

dose of ixabepilone. Both biopsies will be processed in one of three ways: (1) for immunohistochemical staining; (2) for RNA; and (3) for protein isolation, if a sufficient quantity is available. The laboratory correlates on the biopsies will attempt to examine tubulin polymerization, and also seek to probe further the effect of ixabepilone. To that end attempts will be made to examine whether there is evidence of activation of pathways of cell death, initially by examining the activation of PARP, a protein whose cleavage generates fragments that can be measured and are recognized as markers of cell death or apoptosis.

Biopsies will be obtained from all patients only if they can be performed under local anesthesia. General anesthesia will not be used to obtain biopsies that are to be used only for research purposes. In order to process the biopsy in the three ways described above a tru-cut type core biopsy needle must be used. Ideally three core biopsies would be obtained and if possible four. These biopsies may be obtained with the assistance of either a surgical consultant or a member of the interventional radiology staff. As an alternative, a needle aspiration may be obtained with the assistance of the cytology staff or a member of the interventional radiology staff. In the case of a needle aspiration, the sample will only be processed for immunohistochemical staining.

Note: It is recognized that a patient may agree to a first biopsy and then decide to not have a second biopsy. In such a case, the biopsy will nevertheless be processed as planned, although the value of the pre-treatment modification of alpha tubulin in predicting response has not been established.

Biopsies performed for research purposes will only be obtained after the procedure has been explained to the patient, and informed consent has been secured.

3.4.2 Pharmacokinetics  
(not applicable)

3.4.3 Pharmacodynamics

To evaluate the pharmacologic activity of ixabepilone in patients, peripheral blood mononuclear cells (PBMCs) will be evaluated to determine the extent to which ixabepilone induces a shift from unpolymerized tubulin to tubulin in a polymerized state. These samples will only be collected on those patients who undergo research biopsies.

Schedule for blood sample collection for tubulin polymerization assay using peripheral blood mononuclear cells (PBMCs): The ability of ixabepilone to induce tubulin polymer formation in peripheral blood mononuclear cells (PBMCs) will be determined for patients during cycle one, following the first intravenous dose of ixabepilone. A blood sample (8 mL) will be collected prior to the drug infusion, to determine each patient's baseline status of unpolymerized tubulin within lysed PBMC pellets versus tubulin that exists in the polymerized state. Following IV administration of ixabepilone, additional blood samples (8 mL each) will be collected at 1, 8 and 24 hours, relative to the start of the 1-hour infusion on Day One.

One additional sample will be drawn within one hour of the biopsy following Day 4 or Day 5 dosing. The purpose of this blood will be to determine if there exists any correlation between the extent of tubulin polymerization in the tumor sample and in the

blood sample. See Appendix A for further information regarding the handling, storage and tracking of these samples.

### 3.5 ON STUDY EVALUATION

#### 3.5.1 Cycle one

Obtained within one week prior to study entry, unless otherwise indicated.

1. History and physical examination.
2. Laboratory studies: CBC with differential, platelet count, and CHEM 20 Panel.
3. Imaging studies: CT or MRI (obtained within four weeks prior to study entry).

#### 3.5.2 Every restaging cycle

(Following the second, fourth and sixth cycles, and then every third cycle)

1. History and physical examination (for medical record only; not for Research record).
2. Laboratory studies: CBC with differential, platelet count, and CHEM 20 Panel.
3. Imaging studies: CT or MRI of known/suspected areas of disease (for medical record only; not for research record).

#### 3.5.3 Every cycle

1. History and physical examination (for medical record only; not for Research record).
2. Laboratory studies: CBC with differential, platelet count, and CHEM 20 Panel.

#### 3.5.4 Weekly treatment monitoring

1. CBC with differential and platelet count will be obtained twice weekly on Monday/Thursday, or Tuesday/Friday during the first two cycles; unless the ANC falls below 500 cells/mm^3 or the platelet count falls below 50,000 cells/mm^3, in which case every attempt should be made to obtain counts every other day until the ANC is above 500 cells/mm^3 and the platelet count is above 50,000 cells/mm^3. If the ANC and platelet count do not fall below the above-mentioned parameters in the first two cycles, CBCs may be obtained once weekly thereafter.

### 3.6 CONCURRENT THERAPIES

Potential Drug Interactions: Ixabepilone may have a minimal potential to alter the metabolic clearance of drugs that are highly metabolized by CYP3A4. When ixabepilone was incubated with human liver microsomes along with compounds specific for the inhibition of individual cytochrome P450s, significant inhibition was observed only with the CYP3A4 inhibitors (troleandomycin and ketoconazole) suggesting that ixabepilone may be a substrate for CYP3A4 in humans. Data also indicate that the main route of metabolism of ixabepilone is through CYP3A4.

The following strong CYP3A4 inhibitors are prohibited on this study: ketoconazole, itraconazole, clarithromycin, atazanavir, nefazodone, saquinavir, telithromycin, ritonavir, amprenavir, indinavir, nelfinavir, delavirdine, and voriconazole). Other CYP3A4 inhibitors can be given with caution.

A more complete list of CYP3A4 inhibitors is found in Appendix C and should be consulted when making decisions regarding concurrent therapies.

In addition, patients should not drink grapefruit juice while on this study.

### 3.7 SURGICAL GUIDELINES

Elective surgical procedures (dental extractions, mediport placement) for patients enrolled on study will be scheduled during the last week of a cycle in order to avoid the nadir periods for leukocytes and platelets. All procedures should be done only when counts are sufficiently recovered to lessen any risk of infection and or bleeding. Radio-frequency ablation (RFA) will be allowed for symptomatic relief of pain.

### 3.8 RADIATION GUIDELINES

No concurrent radiation therapy will be allowed on study.

### 3.9 OFF TREATMENT CRITERIA

1. Progression of disease during treatment on study protocol. Decisions will be made at the time of restaging (restaging planned after the second, fourth and sixth cycles and then every third cycle). However, if clinically indicated, a decision may be made following the first cycle, after obtaining the appropriate staging studies.
2. Grade 3/4 toxicity lasting greater than 2 weeks or when therapy is judged detrimental to the patient's health.
3. Grade 4 hypersensitivity reaction to drug administration (anaphylaxis).
4. Patient non-compliance or voluntary withdrawal.
5. Discretion of the Principal Investigator.
6. Unacceptable toxicities that have not resolved at time of "off treatment" or "off study" must be followed until stabilization or resolution.

The reason for treatment removal and the date the patient was removed will be documented in the Case Report Form.

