### 3.10 OFF-STUDY CRITERIA

This study does not involve a preset period of monitoring or follow-up after a patient has reached off treatment status. In most cases the Off-treatment and Off-Study dates will be the same. If a patient has a treatment related toxicity, and in the opinion of the PI it is prudent and medically necessary to monitor the patient further, an individual patient may remain on-study, but off-treatment until such time the PI determines it safe to remove them from study.

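### For a starting-dose patient whose ANC or platelet count stays grade 3/4 for more than two weeks, section 3.3.2 sets a dose for the next cycle while section 3.9 item 2 ends treatment, and neither says which prevails

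*Combined protocol and SAP*

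**What the plan says.** **Section 3.3.2 (hematologic toxicity and late cycles).** After cycle 1, day 1 dosing requires an ANC above 1000/mm³ and platelets above 75,000/mm³. On lateness the text says "Doses will be modified if the start of a cycle is delayed more than two weeks", and the table row "Delay in starting cycle > 2 weeks" carries a one-level reduction. For shorter delays, "There will be no dose modification for a delay of two weeks or less". Separate nadir rows also give a one-level reduction, for an ANC of 500/mm³ or less lasting at least 4 days and for platelets of 50,000/mm³ or less. The 4-day row has no upper limit on duration. Nothing in 3.3.2 ends treatment.

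**Section 3.9 (off-treatment criteria).** Item 2 is "Grade 3/4 toxicity lasting greater than 2 weeks or when therapy is judged detrimental to the patient's health". Meeting a criterion means removal: "The reason for treatment removal and the date the patient was removed will be documented in the Case Report Form".

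**Related text.** Section 3.3.1 allows a single reduction, from 6 to 4.5 mg/m²/day, and removes patients whose toxicities continue at the lower level. Section 3.3.3 has its own two-week removal rule, expressly for non-hematologic toxicity. Section 3.10 says "In most cases the Off-treatment and Off-Study dates will be the same".

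**The concern.** Both sections use a two-week limit and both can be triggered by the same low count, but they lead to different actions. One sets a dose for the next cycle and the other stops treatment. Staff who work from the dose-modification section and staff who work from the off-treatment section could treat the same patient differently, each in line with the protocol.

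The first stake is safety, since the patients concerned are those with prolonged myelosuppression. The second is consistency: time on drug would depend on which section was read. Leaving treatment also usually means leaving the study, so for a patient without a response the choice can decide when follow-up for progression ends.

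**Working it through.** The plan gives no figure to reproduce here, so the main check sets the two rules side by side.

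**Step 1. Does item 2 reach blood counts?** Its wording has no qualifier. Section 3.3.3 uses the term non-hematologic where a rule is meant to be so limited. Section 1.2.4, reporting the breast cancer trial on this schedule, lists neutropenia among grade 3 and 4 toxicities. On the document's own usage, item 2 covers counts.

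**Step 2. Apply both rules to a patient at 6 mg/m²/day.**

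| Case | Section 3.3.2 | Section 3.9 item 2 |
|---|---|---|
| A. Count stays grade 3/4 and below the restart threshold, holding back the next cycle by 15 days or more | One-level reduction | Off treatment |
| B. Count is grade 3/4 from day 10 to day 25 of a 21-day cycle (25 − 10 = 15 days), then recovers; delay about 25 − 21 = 4 days | No change for the delay (a nadir row may still give a reduction) | Off treatment |
| C. Count improves below grade 3 within two weeks but stays under the restart threshold; delay over two weeks | One-level reduction | Not met |
| D. Delay over two weeks for a reason other than toxicity | One-level reduction | Not met |

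Cases A and B conflict; C and D do not. Case B, an illustration, arises because the sections count different intervals: 3.9 counts how long the toxicity lasts, and 3.3.2 counts how late the cycle is.

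**Step 3. Patients already at 4.5 mg/m²/day.** No further reduction exists and 3.3.1 already calls for removal if toxicities continue, so they are outside the conflict.

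**Step 4. Dependence on grade cut-offs.** The documents print no CTCAE cut-offs. Case A therefore specifies a count that is both grade 3/4 and below the restart threshold throughout. It does not assume that every grade 3/4 count fails the threshold.

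**Step 5. Possible size.** Inputs:

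- Grade 3/4 neutropenia of 35%, from the 37-patient breast cancer trial on this schedule (section 1.2.4). No platelet figure is given for that trial.
- Per-cohort sample sizes of 12 and 37, and a response rate of 20% under the alternative (section 5.4.1).
- The share of grade 3/4 neutropenia lasting over two weeks is not in the documents. I assume 5% to 10%, for illustration only.

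Full cohort:

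- 0.35 × 37 = 12.95 patients with grade 3/4 neutropenia
- 12.95 × 0.05 to 0.10 = 0.65 to 1.30 with a prolonged episode
- × 0.20 = 0.13 to 0.26 would-be responders, if response is independent of neutropenia

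Stage 1:

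- 0.35 × 12 = 4.2
- 4.2 × 0.05 to 0.10 = 0.21 to 0.42
- × 0.20 = 0.04 to 0.08

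Only a would-be responder whose response had not yet been recorded could alter a cohort's count, so these last figures are upper limits under the stated assumptions.

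**The case against.** The strongest answer is that the sections do different jobs. Section 3.3.2 says what dose to give if a late cycle starts; it does not promise that every delayed patient is re-treated. Section 3.9 decides whether treatment continues. If 3.9 is applied first, 3.3.2 still has work to do in cases such as C and D, and nothing clashes. This reading is possible, but no section states that order and neither refers to the other. Sections 3.3.1 and 3.3.3 also write removal into the dose-modification rules where it is intended, and 3.3.2 does not.

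A second answer is that item 2 was meant for non-hematologic toxicity only, in line with 3.3.3. That too would remove the conflict, but the text does not say it. The two answers resolve case A in opposite directions, which is why the text needs to be settled.

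Investigator discretion (3.9 item 5) permits removal; it does not waive item 2.

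What stands from the other side is the limit on scope. A reader might infer that any cycle more than two weeks late triggers both rules. That is not so, because a delay can outlast the grade 3/4 period or have another cause.

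**Conclusion.** The conflict is real but narrow. It concerns a patient at the starting dose with an ANC or platelet count that stays grade 3/4 for more than two weeks. It is a contradiction between two stated treatment rules and bears on safety and on consistent time on treatment. Probably few patients are affected: about one or fewer per full cohort on the assumed 5% to 10%, a share that has no source in the documents.

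Two stronger inferences are tempting and are not supported.

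- **That the response decisions are at risk.** Pooling both cohorts gives 0.35 × 74 = 25.9 patients with grade 3/4 neutropenia and 1.3 to 2.6 prolonged cases, which looks large beside cut-offs of 1 and 4. But section 5.4.1 decides each cohort separately, and 74 assumes that both pass stage 1. Per cohort, the expected number of affected would-be responders is well below one. No effect on the 1 of 12 or 4 of 37 decisions is shown, and the design's error rates are untouched.
- **That responses would go unobserved.** Section 3.11 keeps following patients in CR or PR who stop the drug, 3.9.1 calls for appropriate imaging on leaving treatment, and 5.2 keeps eligible, evaluable patients in the main response analysis despite early discontinuation. Reduced progression follow-up for non-responders comes from 3.10 and 3.11 and applies to every reason for stopping. This conflict affects only which patients meet it and when.

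**What to change.** Reconcile sections 3.3.2 and 3.9. State in 3.9 item 2 whether it covers hematologic toxicity. If it does, state which section governs when both apply, including when the toxicity lasts over two weeks but the cycle delay is shorter. Name the interval meant in each place (duration of the toxicity or lateness of the cycle), and cross-reference the two sections. Which rule applies is for the clinical team to decide.

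The cost is about one clarifying sentence in each section. Sample size, stopping boundaries and analyses do not change.

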#### 3.9.1 Post-Treatment Evaluation (Upon Meeting Off Treatment Criteria)

1. History and physical examination (for medical record only)
2. Laboratory studies: CBC with differential and platelet count, and CHEM 20 Panel.
3. Chest X-ray.
4. Appropriate diagnostic imaging.
5. ECOG performance status assessment

### 3.10 OFF-STUDY CRITERIA

This study does not involve a preset period of monitoring or follow-up after a patient has reached off treatment status. In most cases the Off-treatment and Off-Study dates will be the same. If a patient has a treatment related toxicity, and in the opinion of the PI it is prudent and medically necessary to monitor the patient further, an individual patient may remain on-study, but off-treatment until such time the PI determines it safe to remove them from study.

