### 3.11 Follow-Up for Progression Free Survival and Duration of Response

An objective of this study is to determine progression free survival and duration of response in patients who achieve either a Complete Response (CR) or a Partial Response (PR). Patients who achieve either a CR or PR and stop receiving study drug will be monitored periodically to follow the course of their response. This follow-up period will vary per patient, but in general will consist of a CT scan every 6 weeks, extending to every 3 to 4 months, per PI discretion. This follow-up may be done here at the NIH Clinical Center, or via the patient's local physician, with scans sent in for inclusion in our trial results. Physical exams, including pelvic exams, will also be done at the same time points.

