## **7 SAFETY REPORTING REQUIREMENTS/DATA SAFETY MONITORING PLAN**

### **7.1 Definitions**

#### **7.1.1 Adverse Events**

An adverse event is defined as any reaction, side effect, or untoward event that occurs during the course of the clinical trial associated with the use of a drug in humans, whether or not the event is considered related to the treatment or clinically significant. For this study, AEs will include events reported by the patient, as well as clinically significant abnormal findings on physical examination or laboratory evaluation. A new illness, symptom, sign or clinically significant laboratory abnormality or worsening of a pre-existing condition or abnormality is considered an AE. All AEs must be recorded on the AE case report form.

All AEs, including clinically significant abnormal findings on laboratory evaluations, regardless of severity, will be followed until satisfactory resolution. AEs should be reported up to 30 days following the last dose of study drug. AEs that are considered treatment related, expected, continuing, but not resolvable by 30 days after treatment completion (e.g., alopecia) will not be followed after the 30-day period.

An abnormal laboratory value will be considered an AE if the laboratory abnormality is characterized by any of the following:

- Results in discontinuation from the study
- Is associated with clinical signs or symptoms
- Requires treatment or any other therapeutic intervention
- Is associated with death or another serious adverse event, including hospitalization.
- Is judged by the Investigator to be of significant clinical impact
- If any abnormal laboratory result is considered clinically significant, the investigator will provide details about the action taken with respect to the test drug and about the patient's outcome.

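### Section 3.10 schedules nothing after the off-treatment evaluation, so an adverse event that first appears between that evaluation and day 30 after the last dose has no planned ascertainment

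*Combined protocol and SAP*

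**What the plan says.** Section 3.10 (Off-Study Criteria) sets the exit rule: "This study does not involve a preset period of monitoring or follow-up after a patient has reached off treatment status". It continues: "In most cases the Off-treatment and Off-Study dates will be the same". Its one stated exception is a treatment-related toxicity that the principal investigator (PI) thinks needs watching. In that case "an individual patient may remain on-study, but off-treatment until such time the PI determines it safe to remove them from study".

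Section 7.1.1 sets the safety window: "AEs should be reported up to 30 days following the last dose of study drug". It also says that all AEs, "regardless of severity, will be followed until satisfactory resolution", apart from expected treatment-related events that cannot resolve by day 30. Section 7.3.4 attaches expedited reporting to events within 30 days of the last dose and, for specified related events, to later ones.

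Section 3.9 item 6 makes follow-up mandatory for unacceptable toxicity that is unresolved at off-treatment or off-study. Section 3.9.1 gives one evaluation on meeting the off-treatment criteria, with history, examination, blood count, chemistry and imaging. The last column of the Appendix B calendar is study termination.

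Section 3.11 concerns responders: "Patients who achieve either a CR or PR and stop receiving study drug will be monitored periodically to follow the course of their response".

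**The concern.** The duty to report AEs runs from the last dose for 30 days. The patient's scheduled contact with the study usually ends on the off-treatment date, which can fall well inside those 30 days. A duty to report does not by itself find events: someone has to ask the patient or receive a report. If nobody is scheduled to ask, new events late in the window are recorded only when the patient or a local doctor happens to report them.

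What is at stake is the completeness of the safety data after the last cycle, and the reliability with which the reporting duties in 7.1.1 and 7.3.4 can be met. The response rate and the two-stage stopping rule are not affected.

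**Working it through.** No sample size, power or event figure bears on this point, so there is no plan figure to reproduce. The check sets the sections side by side and then does day arithmetic.

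**Which events have a planned route into the data?**

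| Event | Governing text | Planned ascertainment |
|---|---|---|
| Present at the off-treatment evaluation | 3.9.1 | Yes, at that evaluation |
| Unresolved at exit | 3.9 item 6; 7.1.1; optional stay on study in 3.10 | Yes, by follow-up |
| First appears after the evaluation, up to day 30 | 7.1.1 and 7.3.4 require a report | None scheduled in 3.9.1, 3.10 or Appendix B |

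Only the third row is a gap. The 3.10 exception does not close it, because it depends on a toxicity already being known.

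**How much of the window is exposed?**

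Inputs:
- The AE window is 30 days from the last dose (7.1.1).
- Dosing is on days 1 to 5 of a three-week cycle (3.2.2), so the last dose of a completed course is on day 5.
- Cycles may be lengthened to 4 or 5 weeks after cycle 6 (3.1).
- A delay of up to two weeks in starting a cycle is allowed without dose modification (3.3.2).
- Progression decisions are made at restaging (3.9 item 1).

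Let d be the cycle day on which the patient goes off treatment and off study. Then

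uncovered days = max(0, 30 − (d − 5)).

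| Exit scenario | d | Days since last dose | Uncovered days of 30 |
|---|---|---|---|
| On the last dosing day | 5 | 0 | 30 |
| Last day of a 21-day cycle | 21 | 16 | 30 − 16 = 14 |
| Planned start of the next cycle | 22 | 17 | 30 − 17 = 13 |
| After a 28-day cycle | 29 | 24 | 30 − 24 = 6 |
| After a 35-day cycle, or a 21-day cycle plus a two-week delay | 36 | 31 | 0 |

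The values of d are assumptions. The documents do not fix the interval from last dose to off-treatment, and they give no frequencies for the scenarios.

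**The case against.** The strongest reply is that off-study status does not end the AE duties. The 7.1.1 window runs from the last dose whatever the off-study date, and nothing in the protocol says that AE recording stops at exit. Section 3.9 item 6 expressly continues past off-study. Section 6.3.3 asks every patient to have a local physician who will monitor for complications. All of this stands, and it settles the matter for toxicity known at exit. It does not provide a way to find a new event: item 6 needs an existing toxicity, and 6.3.3 schedules no report from the local physician back to the study.

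Three stronger readings are tempting, and the documents do not support them.

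- A reader might infer that late toxicity in general goes uncollected, or that there is no follow-up at all. Section 3.10 denies only a preset period. Section 3.9.1 requires an evaluation at exit, and 3.9 item 6 and 7.1.1 require follow-up of what is found.
- A reader might infer that patients typically leave during the blood-count nadir. For the usual exit at restaging this does not follow. Section 3.7 places elective procedures in the last week of a cycle in order to avoid the nadir, and 3.9.1 includes a blood count. The worry is limited to patients who leave soon after dosing, for example on withdrawal or after anaphylaxis.
- A reader might take 3.11 as further proof of a safety gap. Section 3.11 concerns response data. Because 3.10 speaks of most cases, 3.11 can be read as a specific exception for responders. The two sections should be cross-referenced, since 3.10 names only toxicity as a reason to stay on study, but this says nothing about AE capture.

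**Conclusion.** The point holds in a limited form. Sections 3.10 and 7.1.1 do not fit together, and AEs that first appear between the off-treatment evaluation and day 30 have a reporting duty but no scheduled ascertainment. For exit at the end of a 21-day cycle the exposed period is about 13 to 14 of the 30 days. Across the scenarios above it runs from 0 to 30 days.

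The enrollment ceiling of 76 bounds the number of patients who could be affected. It is not an estimate, because patients with extended or delayed cycles may have no exposed days and those with unresolved unacceptable toxicity are already followed. The conclusion assumes that the off-study date usually equals the off-treatment date, as 3.10 says, and that no contact is arranged outside the protocol. It is a safety-data point that should be corrected. It does not affect the primary endpoint.

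**What to change.** - Reconcile 3.10 with 3.9 item 6, 3.11 and 7.1.1, so that the exit rule states which follow-up duties continue after off-treatment.
- Add to 3.10 and Appendix B one documented contact at about day 30 after the last dose, by telephone or through the local physician, with the result recorded on the AE form. It would apply to patients who have not withdrawn consent.
- State in 3.10 that patients with a complete or partial response who stop drug without progression stay in follow-up under 3.11.

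The cost is protocol wording, one call per patient (at most 76) and a slightly later off-study date for some. Section 7.4 already gives research nurses a part in monitoring. The change concerns data collection only and does not touch dosing or treatment.
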